5 STUDY PARTICIPANTS

The study will be undertaken within 2 settings:

- Sub-study 1: Asymptomatic Testing Sites (ATSs) and
- Sub-study 2: NHS primary care staff, and Adult Social Care staff, visiting professionals and visitors.

We expect widespread usage of the webservice during sub-study 2 by a broad range of, healthcare professionals within the NHS cohort and by an equally diverse group of care home staff and visitors from the general public.

User age ranges across all cohorts will likely be 18-65 years old (care home visitors may also be outside of this range), representing all gender identities and a wide cross-section of ethnicities.

Geographic spread will be largely dependent on the number of Asymptomatic Test Sites, NHS trusts and Care Homes that participate in the pilot but will represent all English regions.

Inclusion Criteria:

- Participant is willing to participate in the study and agrees with the privacy statement
- Aged 18 years or above
- Adolescents aged 12-17 (self-test and report with adult supervision)
- Without any common COVID-19 symptoms
- Able (in the Investigators opinion) and willing to comply with all study requirements
- Children under 12 (should be tested and reported by an adult)

Exclusion Criteria

The participant may not enter the study if ANY of the following apply:

- Participant does not agree with privacy statement.
- Has any common COVID-19 symptoms.
- Any other significant disease or disorder which, in the opinion of the Investigator, may either put the participants at risk because of participation in the study, or may influence the result of the study, or the participant's ability to participate in the study.

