3 To assess the effectiveness and efficiency of the digital service in its intended use setting by the intended user population (reference to the SIU	3) At least 95% of effectiveness and efficiency will confirm the usability of the image-capture element of the digital service, regardless of the device used for			
	image capture (i.e., phone, tablet)			
4) To assess the performance of the				
algorithm in identifying void tests (i.e.	1) The 9/ of tests reported as youd by			
tests performed incorrectly) where a	4) The % of tests reported as void by			
tests performed incorrectly), where a	the algorithm will be compared to the %			
control line is missing.	reported by individuals as void (study			
	participants will be asked to submit photos			
	of void tests. In addition, where there is a			
	discrepancy (whereby the user's response			
	differs from an algorithm's read, these will			
	be referred to an independent off-line			
	review of the image. The % of those			
	images correctly identified as yoid will be			
	reported			
	reponea.			

5) To assess the implication of the types of devices used (Tablets, PCs, phones of various models) on the image quality and therefore implication for algorithms	5) A breakdown of the device types, with % of images which meet the quality requirements defined above, particularly linked to image quality (resolution, pixels, lighting/flash)

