APPENDIX 2: HUMAN FACTORS AND USABILITY STUDY DESIGN PROTOCOL

Background and Rationale

This study concerns the use of an AI reader function embedded within a digital reporting service for interpreting Covid-19 lateral flow tests at point of use.

The end assumptions and hypotheses for the final product are:

Better user experience - The user will not have to interpret the result and enter their result, so using the AI reader will reduce anxiety for the user to correctly interpret the result.

Greater accuracy - The AI interpreted result will be more accurate than the selfreported result as it will reduce human error and fraud. This will help to identify more asymptomatic test subjects and reduce the transmission rate of the virus.

This pilot will improve our understanding of the use of the online "photograph taking process" in practice and to determine whether the product is easy to use and safe in the intended context of use.

Aims

- To understand who the users, their experience, the tasks they have to perform and the contexts within which they work
- To assess certain human factors (lay and professional user) associated with the use of the decision support software in order to understand the usability and accessibility of the service
- Assess completion of tasks
- Gather subjective data on safety and ease of use
- Identify any use errors
- Evaluate the user experience and user expectations

Tasks

1. Take a photograph of the lateral flow test strip

Subtasks of task 1.0

1.1a User opts out of providing a photograph

Digital

1.1b User opts in to provide a photograph image of the test strip

1.2 User reads guidance on how to correctly take a photograph image of the test strip

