1.6 User checks all answers and reports result

Participants

Participants for the trial will be recruited from two use case groups:

- Adult Social Care
- Primary Care (Community pharmacy, NHS Optometry, NHS Dental and General Practice)

Methodology

A survey will be distributed via comms teams to the use case groups to be completed during the trial period.

This survey will collect data on the participant's themselves and their experience of using the product during the trial, as well as operate as a recruitment tool for qualitative interviews.

Interviews to be conducted with 15 participants from each use case group (Adult Social Care and Primary Care) who consent to be contacted for a follow-up interview. The interview will cover their survey responses in more depth, and to attempt to establish the root cause of any user errors or difficulties encountered.

Adobe analytics will also be used to identify user interactions across the digital journey, including any drop off points.

Survey Questions

User Profile

- Sector of work
- Job Title
- Context of Use
- Gender
- Age
- Ethnicity
- Internet Use
- Accessibility software used
- Disabilities or long-term health conditions

Usability Questions

- How many Covid-19 Lateral Flow tests have you taken so far during the trial? (If you are a nominated person responsible for reporting all staff lateral flow test results, please tell us how many test results you have reported in total)
- Of these, how many times did you take and upload a photo of the lateral flow test strip?
- If you did not take and upload a photo every time, please tell us why
- Did you ever have to try more than once to take and upload a photo?
- How many times did you have to try more than once?
- If you had to try more than once, at any time, please tell us more about what happened
- How easy did you find it to take and upload a photo of the lateral flow test strip?

Interview Script

Welcome and Intro

- Purpose
- Consent and confidentiality
- Recording
- Observers

Recap

Refer back to their survey answers for prompts:

- Can you tell me a little bit about how you found taking and uploading a photo of your test?
- What device did you use?
- Where were you when you were taking the test/taking the photo?
- How did you approach it?
- Did you experience any difficulties doing this?
- Did you need to get any help or assistance from anyone else?

Improvements

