- What benefits (if any) do you see in taking a photo of the lateral flow strip and uploading it?
- If you were to do this process again in the future, would you take a photo of the test strip on those occasions?
- If not, why not?
- How might we improve the process of taking and uploading a photo of the lateral flow test device?

Usability Metrics

The ISO 9241-11 standard defines usability as "the extent to which a product can be used by specified users to achieve specified goals with effectiveness, efficiency and satisfaction in a specified context of use".

The ISO/IEC 9126-4 Metrics recommends that usability metrics should include:

- Effectiveness: The accuracy and completeness with which users achieve specified goals
- Efficiency: The resources expended in relation to the accuracy and completeness with which users achieve goals.
- Satisfaction: The comfort and acceptability of use.

Usability Metrics for Effectiveness

a) Completion Rate

Effectiveness can be calculated by measuring the completion rate – uploading image of the completed LFD test. Referred to as the fundamental usability metric, the completion rate is calculated by assigning a binary value of '1' if the test participant manages to complete a task and '0' if he/she does not.

Effectiveness can thus be represented as a percentage by using this simple equation:

$$Effectiveness = \frac{\text{Number of tasks completed successfully}}{\text{Total number of tasks undertaken}} \times 100\%$$

Our aim for a completion rate of at least 95%

b) Number of Errors

This measurement involves counting the number of errors the study participant makes when attempting to take and upload the image.

Usability Metrics for Efficiency

Efficiency is measured in terms of submitted image quality. The Efficiency rate is calculated by assigning a binary value of '1' if the uploaded image was successfully interpreted by AI, and value of '0' will be assigned if AI failed to interprets the image.

Efficiency can be represented as a percentage by using this simple equation:

Efficiency = Number of images successfully analysed by AI X 100%

Total Number of images submitted for AI interpretation

Our aim for an efficiency rate of at least 95%

Usability Metrics for Satisfaction

a) Task Level Satisfaction

After users attempt a task (irrespective of whether they manage to achieve its goal or not), they will be given a questionnaire so as to measure how difficult that task was.

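### Section 5's ability and disorder criteria conflict with Sub-study 2's aim of assessing usability in the intended user population and, if applied, would bias the 95% rates upward by an unknown amount

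*Protocol*

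**What the plan says.** Section 5 names the two settings and then gives a single set of inclusion and exclusion criteria. One inclusion criterion is "Able (in the Investigators opinion) and willing to comply with all study requirements". One exclusion criterion covers a significant disease or disorder that, in the investigator's opinion, puts the participant at risk, or "may influence the result of the study, or the participant's ability to participate in the study". Neither is limited to one sub-study.

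Section 3 sets a usability objective covering the effectiveness and "efficiency of the digital service in its intended use setting by the intended user population". Its success statement is "At least 95% of effectiveness and efficiency will confirm the usability of the image-capture element of the digital service". Section 12.2 defines completion as an image submitted by the user and an interpretation received from the algorithm. Appendix 2 repeats the target ("Our aim for a completion rate of at least 95" per cent), scores each task 1 or 0, and divides by the tasks undertaken. Its efficiency rate, also with a 95% aim, is the share of submitted images that the AI interprets.

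Appendix 2 also sets out to assess human factors "in order to understand the usability and accessibility of the service". Its survey profile asks about accessibility software and "Disabilities or long-term health conditions".

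Section 6 recruits Sub-study 2 by filtering answers given in the web registration journey. Section 12.3 concedes that these users may be more skilled than the general population and expects demographic data to correct this in part.

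**The concern.** The two criteria are standard wording that suits an accuracy study, where a person's difficulty in following the procedure is noise. In a usability study that difficulty is part of what is being measured. Section 10 says that the only new process is using a mobile device to capture the image. For Sub-study 2, ability to meet the study requirements therefore overlaps heavily with ability to do the task that is scored.

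A person whose sight or dexterity makes a failed photograph more likely could be kept out on either criterion. These are illustrations; the protocol names no condition. Such people belong to the intended user population in Section 3 and are the ones an accessibility aim most needs. At stake is what a 95% result would mean: usable by intended users, or usable by those judged able beforehand. The results go to the regulator (Section 17) in support of use in mass testing (Section 2).

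**Working it through.** **No figure to reproduce.** The 95% is a benchmark. The protocol gives no sample size, error rate or variance behind it for Sub-study 2.

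**The texts side by side**

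| Question | Entry rule (Section 5) | Objective and measures (Section 3, Section 12.2, Appendix 2) |
|---|---|---|
| Who is studied? | People judged able, without a disorder that could affect the result or participation | Intended users in the intended setting |
| Role of difficulty with the task | Possible ground for non-entry | The outcome: completed 1, not completed 0 |
| Users with disabilities | May be excluded, case by case | Expected among survey respondents; accessibility is an aim |

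The completion denominator is tasks undertaken and the efficiency denominator is images submitted. A person who never enters contributes to neither.

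**Direction and size.** Let E be the completion rate among eligible users, f the share of intended users kept out (strictly, the share of tasks they would have undertaken), and c the completion rate they would have had. Then:

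- rate in all intended users = (1 − f) × E + f × c
- overstatement = f × (E − c)

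The overstatement is positive whenever c is below E and f is above zero. The documents give none of the three quantities, so all values below are assumptions. With E = 95%:

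| f | c | Rate in all intended users | Overstatement (points) |
|---|---|---|---|
| 0 | any | 95.0% | 0 |
| 1% | 75% | 0.99 × 0.95 + 0.01 × 0.75 = 94.8% | 0.2 |
| 5% | 75% | 0.95 × 0.95 + 0.05 × 0.75 = 94.0% | 1.0 |
| 5% | 50% | 0.95 × 0.95 + 0.05 × 0.50 = 92.75% | 2.25 |
| 10% | 50% | 0.90 × 0.95 + 0.10 × 0.50 = 90.5% | 4.5 |
| 20% | 0% | 0.80 × 0.95 = 76.0% | 19 |

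A starting value slightly above the benchmark, E = 96%, shows how the pass or fail result can move:

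- f = 3%, c = 60%: 0.97 × 0.96 + 0.03 × 0.60 = 94.9%, below target.
- f = 5%, c = 80%: 0.95 × 0.96 + 0.05 × 0.80 = 95.2%, still on target.
- The rate falls below 95% once f exceeds (0.96 − 0.95)/(0.96 − c). That is 0.01/0.36 = 2.8% at c = 60%, and 0.01/0.16 = 6.25% at c = 80%.

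**Can demographics repair it?** Section 12.3 relies on them for partial correction. Reweighting works from people who were observed. It cannot supply outcomes for people refused entry because of expected difficulty.

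**The case against.** The strongest reply is that the criteria may do nothing in Sub-study 2. Section 6 recruits by web filter, Appendix 1 describes that filter as work setting or care-home link, and Section 7 takes consent through a privacy statement. No step has an investigator judge ability. This stands, and it means the effect may be nil. It does not remove the contradiction: the protocol states an entry rule that conflicts with its target population and does not say that the rule is inactive.

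Three further points also stand and limit the claim.

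- A reader might infer that the 95% rate is conditioned on actually being able to do the task. It is not. Selection would be on a prior opinion, and Appendix 2 scores enrolled users who fail as 0.
- A reader might also infer that failing users could be removed afterwards as ineligible. No text provides for this. Section 5 words the exclusions as conditions of entry, and the removal stated for Sub-study 2 is of non-Innova devices.
- Being unable to photograph alone is not clearly being unable to comply. Appendix 2 lists an opt-out and repeat attempts, the interview asks about help from others, and Section 5 admits children tested and reported by an adult.

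The survey items on disability and accessibility software show that such users are not barred as a group. Accessibility is an aim without a target, so the bias concerns the completion and efficiency rates only. Section 12.2 places the primary objective in Sub-study 1, which this point does not touch, and Appendix 1 plans a further post-market usability study. An extra table by disability might be thought a matter for an analysis plan, but Section 12 says no separate one is in use.

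**Conclusion.** The point holds as an inconsistency between Section 5 and the Sub-study 2 objectives. Followed as written, the two criteria select on predicted ability to do the measured task, and the completion and efficiency rates would be biased upward if those kept out would succeed less often.

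The documents do not allow the size to be fixed. It is zero if the criteria are never applied. Over the assumed ranges (f from 1% to 20%, c from 0 to 75%, E = 95%) it runs from 0.2 to 19 points. The upper end is an extreme combination, and none of these values has a source in the protocol. They show sensitivity, not a forecast that the study would wrongly pass.

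This should be corrected because the change is cheap and the benchmark is meant to confirm usability. It does not threaten the primary accuracy objective. Confidence is medium, mainly because the protocol leaves open whether the criteria operate in Sub-study 2.

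**What to change.** For Sub-study 2 only:

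1. Remove the investigator-judged ability wording from the inclusion criteria, and the clauses on influencing the result or the ability to participate from the exclusion criterion. Keep the participant-risk clause and the privacy agreement.
2. Report the number of users excluded on eligibility grounds, with reasons.
3. State that every user who starts the task stays in the completion denominator. This makes explicit what the Appendix 2 scoring already implies.
4. Summarise the survey usability answers separately for respondents who declare a disability or use accessibility software. Both items are already collected.

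The cost is an amendment to two eligibility lines, two reporting sentences and one extra table. The downside is a possibly slightly less favourable rate, which would describe the population named in Section 3.

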6 RECRUITMENT AND STUDY SITES

We will be using images captured at Asymptomatic Testing Sites by trained operatives as part of the ATS LFD current registration and reporting service. We will recruit NHS staff and Adult Social Care staff and visitors for the pilot cohort by filtering responses given during the current Self-report LFD web registration journey. For NHS use case, we have the opportunity to filter based on NHS setting (eg General Practice, Dentistry, Acute (hospital) trust etc).

For Adult Social Care homes, we will filter on the Adult Social Care homes that have agreed to be part of the Sub-study 2. We will select such care homes that have a significant number of full-time care staff in order to provide the scale of staff and visitors required for the study.

7 INFORMED CONSENT

User consent for using the photo is covered in the privacy statement. https://www.gov.uk/government/publications/coronavirus-covid-19-testingprivacyinformation/testingfor- coronavirus-privacy-information-quick-read--2

8 DEFINITION OF END OF STUDY

The end of trial is the point at which all the data has been entered and queries resolved. This is anticipated to be in March 2021.

9 WITHDRAWALS

Participants are free to withdraw their consent from this study at any time, for any reason. There is no obligation to give the reason for withdrawal. If the participant is withdrawn due to any adverse event (LFT device or study related), the investigator

will arrange for follow-up visits or telephone calls until the adverse event has resolved or stabilised.

10 RISK ANALYSIS

The anticipated risks associated with this study are given in the Risk Assessment Table (see Appendix 1).

The risk-to-benefit assessment is preferable to a ratio and is based on anticipated risks associated with this study and how harm is minimised through the careful study design and importance of the objectives.

This describes all perceived risks to which the participants will be exposed as a result of their participation in this study and how these risks will be minimised. The risks are considered to be low-medium and do not outweigh the benefit, to enable us to continue with the study.

A FMEA analysis based on the features and functionality available for the study is being prepared to assess the potential risks which can arise during the study and will be finalised according to risk management procedure QP08 RMF.

Separate FMEAs are available for camera interpretation of Lateral Flow Testing software and web-based tests results reporting process.

We are utilising existing use cases with established operating procedures which are clinically safe e.g., use of PPE and where the appropriate approvals for use of the LFDs already exist.

The study does not introduce any new additional processes with the exception of the use of a mobile device to capture the image.

We are not looking to introduce new LFD use cases to facilitate this trial.

11 SAFETY REPORTING

As identified within Department of Health and Social Care Quality Management System (QMS) the safety reporting process is controlled under the QP21 Medical Device Reportability Requirements and FSCA Procedure.

11.1 Definitions⁵

Adverse Event (AE):

Any untoward medical occurrence, inappropriate patient management decision, unintended disease or injury, or untoward clinical signs in subjects, users or other persons, with any connection to study related activities, whether or not related to the IVD medical device under investigation.

Adverse Device Effect (ADE):

Adverse event related to the use of an IVD medical device under investigation.

Serious Adverse Event (SAE):

Adverse Event that led to any of the following

- a) death,
- b) serious deterioration in the health of the subject, users, or other persons as defined by one or more of the following:
 - 1. a life-threatening illness or injury, or
 - a permanent impairment of a body structure or a body function including chronic diseases, or
 - 3. in-patient or prolonged hospitalization, or
 - medical or surgical intervention to prevent life-threatening illness or injury, or permanent impairment to a body structure or a body function,

5. foetal distress, foetal death, a congenital abnormality, or birth defect including physical or mental impairment

Serious Adverse Device Effects (SADE):

Adverse device effect that has resulted in any of the consequences characteristic of a serious adverse event.

Unanticipated Serious Adverse Device Effect (USADE):

Serious adverse device effect which by its nature, incidence, severity or outcome has not been identified in the current version of the risk analysis report.

Device deficiency:

Inadequacy of a medical device with respect to its identity, quality, durability, reliability, usability, safety or performance, such as malfunction, misuse or use error and inadequate labelling.

Malfunction:

Failure of an IVD medical device under investigation to perform in accordance with its intended use.

11.2 Reporting of AE

All study personnel will be aware of the requirements for reporting adverse events and will be responsible for informing Study Chief Investigator and DHSC's Regulatory Affairs Department if they become aware of a suspected event.

Study Chief Investigator and DHSC's Regulatory Affairs Department will review each incident to check if it meets reportability requirements and, if so, will identify the Page 22 of 41

authorities to whom the incident needs to be reported and will perform this report in conformity with the process and timescales required by the regulatory authorities, as follows:

- a SAE which indicates an imminent risk of death, serious injury, or serious illness and that requires prompt remedial action for other patients/subjects, users or other persons or a new finding to it - immediately, but not later than 2 calendar days after awareness by sponsor of a new reportable event or of new information in relation with an already reported event.
- any other reportable events or a new finding/update to it: immediately, but not later than 7 calendar days following the date of awareness by the sponsor of the new reportable event or of new information in relation with an already reported event.

If the incident is deemed to be a reportable adverse event (AE) the DHSC Regulatory Affairs Department will initiate an AE reporting process as per QP21.

All AE's occurring during the study observed by the investigator or reported by the participant, whether or not attributed to the device under investigation will be recorded in the AE Form (QP20-F01).

The relationship of AEs to the device will be assessed by a medically qualified investigator or the sponsor/manufacturer and will be followed up until resolution or the event is considered stable.

All ADE that result in a participant's withdrawal from the study or are present at the end of the study, should be followed up until a satisfactory resolution occurs.

